7. STUDENT RESEARCH

When a student acts as principal investigator, a faculty sponsor signature is required on the application form.

N/A

8. RENEWAL APPLICATIONS

When the submission is a Renewal Application, include a summary of the research activities during the previous granting period specifically addressing: number of subjects studied and any adverse reactions encountered, benefits which have been derived, any difficulty in obtaining subjects or in obtaining informed consent, and approximate number of subjects required to complete the study.

N/A

9. PAYMENTS

If subjects are to be paid in cash, services, or benefits, include the specific amount, degree, and basis of remuneration.

All participants will have the opportunity to compete for a cash prize in each round (one prize ranging from \$100 to \$500) as well as cumulative cash prizes to be awarded to top scorers in each age-group (1st place=\$1000; 2nd place=\$500, 3rd place=\$250) at the end of the game. These prizes will take the form of Visa gift cards. Winners will be notified via text message and email and will be asked whether they prefer to have an electronic Visa gift card emailed to them or have a physical version mailed to them. Those who elect to have a physical version mailed will be asked to provide their postal address.

Evaluation study participants (N=500) who play the majority of rounds and complete the follow-up survey will receive \$40 in e-gift cards of their choice (iTunes, Amazon, Target or Starbucks). Consistent with other university and NIH sponsored research conducted by our team, giftcards will be sent via GiftBit. Players will receive a \$20 giftcard for completion of rounds and a \$20 giftcard for completion of the post-competition feedback survey.

10. PSYCHOLOGY SUBJECT POOL

When students from the Psychology Subject Pool (PSP) are to be involved as subjects, permission must be obtained from the PSP prior to running subjects.

Forms are available from the Psychology Office in [name]. It is not necessary to inform the IRB of approval from the PSP, however the PSP requires IRB approval prior to permission for using the pool being granted.

N/A

11. QUALIFICATIONS AND TRAINING

Describe the qualifications of, or method of training and supervision afforded student experimenters. This includes past experience, type and frequency of student/sponsor interactions during the experiment, and Human Subjects Protections Training.

N/A

12. RANDOMIZATION

Describe criteria for assigning subjects to sub-groups such as "control" and "experimental."

As described previously, Qualtrics Research Suite's automated randomizer will be used to randomize evaluation study participants to a PNF condition at the point of study enrollment in round 3.

Randomization determined the sequence of topics on which participants received detailed results across intervention rounds 3 and 4: alcohol+coping, alcohol+control, or control only. Members of the research team will be blinded to participant condition assignment, and the study participants will not be aware that any sort of randomization was taking place. Rather, when detailed results were sent at the end of each round, players will be prompted to choose among 3 animated, graphical doors to determine the 1 to 2 round topics on which they would view detailed results. Although the results topics will be truly determined via chance in most rounds of the competition, the doors of evaluation study participants will be fixed to open to their randomly assigned feedback topics regardless of the door they selected in rounds 3 and 4. Upon completing the feedback survey at the end of the competition, participants will be debriefed regarding the study's research questions and the fixed sequences of health or control feedback they were randomized to receive in rounds 3 and 4.

13. USE OF DECEPTION

If the project involves deception, describe the debriefing procedures that will be used.

Include, verbatim, the following statement in the consent form: "Some of the information with which I will be provided may be ambiguous or inaccurate. The investigator will, however, inform me of any inaccuracies following my participation in this study."

Although none "of the information which participants will be provided will be ambiguous or inaccurate" under any circumstances, the fixed nature of the feedback selection mechanism encountered by Evaluation Study participants in Rounds 3 and 4 may be considered minor deception. Thus, upon completion of the follow-up survey intervention study participants will be debriefed regarding the non-random nature of these mechanisms. (See APPENDIX D for debriefing statement)

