Qualtrics Research Suite's automated randomizer will be used to randomize evaluation study participants to a PNF condition at the point of study enrollment in round 3. Randomization will determine the sequence of topics on which participants will receive detailed results across intervention rounds 3 and 4: alcohol+coping, alcohol+control, or control only. Members of the research team will be blinded to participant condition assignment, and the study participants will not be aware that any sort of randomization was taking place. Rather, like in other rounds, when detailed results are sent players will be prompted to choose among 3 animated, graphical doors to determine the topics on which they will view detailed results. Although the results topics will be truly determined via chance in most rounds of the competition, the doors of evaluation study participants will be fixed to open to their randomly assigned feedback topics regardless of the door they selected in rounds 3 and 4. Upon completing the feedback survey at the end of the competition, participants will be debriefed regarding the study's research questions and the fixed sequences of health or control feedback they were randomized to receive in rounds 3 and 4. See Appendix D for the Debriefing Statement.

Replay Bonus Rounds 7 and 8.

The last 2 rounds of the competition, 7 & 8, will feature new question topics as well as previously assessed REPLAY BONUS topics which will allow all players to boost their scores by placing very large bets on a topic they already received feedback on and very small bets for topic on which feedback has not yet been delivered. PNF will be delivered for the new topics assessed in each round but will not be repeated for REPLAY BONUS topics. Instead a single screen will reveal the points earned from REPLAY BONUSES. Importantly, answers to REPLAY BONUS questions in Round 7 among intervention study participants' will act as the 2 month post-intervention follow-up for the purpose of the evaluation study RCT.

Competition Conclusion

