Following the announcement of winners after Round 8, the LezParlay competition will be over. A special sequence of screens follow for Evaluation Study Participants. Study participants will be provided the opportunity to complete the follow-up survey for the evaluation study on screen or have the link to emailed/texted to them so that they can complete it later. Upon submitting the short follow-up survey, participants will be prompted to select a \$40 electronic gift card (Amazon, Target, Starbucks, etc.) to receive via email. A final screen will thank them for their time and debrief them about the fixed nature of the spinners that selected their detailed results topics in Rounds 3 and 4. Text will reveal that this was necessary in order to examine the perceptual and behavioral impacts of different combinations of detailed results delivered in these rounds. Questions to be featured in Intervention and Replay Bonus Rounds are presented in Appendix C. A list of potential control/filler stereotype related questions to comprise other rounds of play also follow in Appendix C. APPENDIX D also provides the Evaluation study follow-up survey and debriefing statement.

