As the LezParlay collects all round data through styled Qualtrics surveys fully embedded into the app, all data is protected by Transport Layer Security (TLS) encryption (also known as HTTPS), which is a protocol that ensures privacy between communicating applications and their users on the Internet. Also used to secure bank and credit card transactions online, TLS ensures that no third party may

eavesdrop or tamper with submitted data. Further, after data collection concludes and all personalized feedback, scores, and incentives, have been received by participants, user photos and identifying information will be destroyed. Only datasets containing de-identified LezParlay Round data will be downloaded from Qualtrics for analysis, password protected, and stored securely on HeadsUp's internal, further password protected server. Thus, these double password protected files will only be accessible to the PI ([name]) and Project Director ([name]).

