The ability to compete as a couple against other couples			
The ability to send other players a "wink" or "nod"			
The ability to message other players			

Did you find taking part in the competition to be beneficial to you at all?

No

Yes

[IF YES]

[figure not shown]

Great! Please use the text box below to briefly describe how the competition was beneficial for you

Do you any other ideas about how LezParlay might be improved?

What would you like to see be different in the next version?

Last thing, we promise! Now that the summer is ending,
please answer the 5 drinking questions a final time.

SINCE THE BEGINNING OF JULY, ON AVERAGE, HOW MANY DAYS PER WEEK
HAVE **YOU** DRANK?

SINCE THE BEGINNING OF JULY, ON AVERAGE, HOW MANY DRINKS HAVE **YOU** HAD EACH
DAY YOU DRANK?

SINCE THE BEGINNING OF JULY, ON THE DAY YOU DRANK THE MOST, HOW MANY DRINKS DID YOU HAVE?

0 1 2 3 4 5 6 7 8 9 10 11 12+

HAD A HANGOVER OR ILLNESS

GOT IN A PHYSICAL OR VERBAL FIGHT

HAD PROBLEMS WITH GF/PARTNER

MISSSED A SOCIAL ENGAGEMENT OR EVENT

HAD PROBLEMS WITH FRIENDS OR FAMILY

PERFORMED POORLY AT WORK/SCHOOL

HAD PROBLEMS WITH MONEY

HAD AN UNWANTED OR REGRETTABLE SEXUAL EXPERIENCE

SINCE THE BEGINNING OF JULY, HOW MANY OF THE 8 THINGS ABOVE HAVE YOU EXPERIENCED DUE TO DRINKING/PARTYING?

SINCE THE BEGINNING OF JULY, WHEN YOU'VE EXPERIENCED STIGMA OR NEGATIVE EMOTIONS WHAT % OF THE TIME DID YOU DRINK ALCOHOL IN AN EFFORT TO FEEL BETTER?

0 10 20 30 40 50 60 70 80 90 100

[End of Survey Debriefing Statement]

A FINAL THANKS & DISCLOSURE...

Thanks again for helping us evaluate LezParlay! Before you go we wanted to give you some more information about the detailed results you received in the LezParlay as an Official Tester. In addition to getting your feedback and ideas for the next version of the competition, another goal of this study was to evaluate whether delivering results for health-related topics in LezParlay had any benefits for players' health and well-being. To fully examine this, we had to make sure that balanced groups of Official Testers received more and less health-related feedback.

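### Debriefing is tied to completing the final survey, so the protocol as shown gives no debriefing route for randomised women who do not complete it

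*Protocol*

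**What the plan says.** Section 3 (Procedures) uses an automated randomizer to "randomize evaluation study participants to a PNF condition at the point of study enrollment in round 3". In Rounds 3 and 4 the doors of study participants open to their assigned topics whichever door they pick. Sections 3 and 12 add that participants will not know that they were randomised.

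Debriefing is described in these places:

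- Section 3, intervention rounds: "Upon completing the feedback survey at the end of the competition, participants will be debriefed regarding the study's research questions", together with the fixed feedback sequences. Section 12 (Randomization) repeats the rule.
- Section 3, Competition Conclusion: after the survey is submitted and a gift card chosen, "A final screen will thank them for their time and debrief them about the fixed nature of the spinners". The word spinners is read here as the same mechanism as the doors.
- Section 13 (Use of Deception), which concedes that the fixed mechanism might count as a mild deception: "upon completion of the follow-up survey intervention study participants will be debriefed regarding the non-random nature of these mechanisms".
- Appendix D prints the text as the "End of Survey Debriefing Statement".

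Under Competition Conclusion a woman may also have the survey link sent to her "so that they can complete it later".

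Section 5 (Confidentiality) lists email address and mobile number among the identifiable data. Once data collection has ended and feedback, scores and incentives have been delivered, "user photos and identifying information will be destroyed".

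**The concern.** The protocol chooses debriefing as its answer to the concealed mechanism, then makes it depend on a step that participants are free not to take. A woman who stops playing, withdraws, or takes the survey link and never uses it has no stated way of being told.

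More than a door animation is withheld. Section 3 describes a consent screen that presents the aim as evaluating the impact and format of the results and collecting player feedback. It leaves the study's research questions and the fixed sequences to the debriefing. On the text shown, the debriefing is therefore where a participant first learns that she was randomised and that health effects were under test.

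What is at stake is participant protection. The gap would also become permanent, because the contact details needed to close it are removed under a rule that does not mention debriefing.

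**Working it through.** The protocol gives no figure for this point, so there is none to reproduce. The check sets the passages side by side.

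**1. Is survey completion the only trigger?** Section 3 (twice), section 12 and section 13 each tie debriefing to completing or submitting the survey, and Appendix D puts the text at its end. These places agree. No other part of the protocol as shown provides a debriefing for a participant who leaves before that point.

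**2. Does the deferral option help?** No. The emailed or texted link leads to the survey. A woman who never opens or submits it does not reach the debriefing.

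**3. Is non-completion foreseeable?** Yes. Randomisation is in Round 3 and the survey follows Round 8, so 8 − 3 = 5 further rounds of a monthly game come between. Section 9 (Payments) offers \$20 for rounds and a separate \$20 for the survey, which treats the survey as a distinct step that some may not take.

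**4. Does the destruction rule protect the route?** No. The conditions in section 5 are the end of data collection and receipt of feedback, scores and incentives. Debriefing is not among them.

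**5. Who is affected?** Two groups should be kept apart:

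- Randomised women who opened at least one fixed door and did not complete the survey. They met the concealed mechanism.
- Randomised women who never opened their Round 3 or 4 results, or skipped them as section 4 (Risks / Benefits) allows. They may not have met a fixed door, but they were randomised without being told.

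**6. Scale.** The protocol plans 500 evaluation participants and states no completion rate, so the rates below are assumptions.

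| Assumed survey non-completion | Women without a stated debriefing route |
|---|---|
| 10% | 500 × 0.10 = 50 |
| 20% | 500 × 0.20 = 100 |
| 30% | 500 × 0.30 = 150 |

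At each assumed rate the count covers both groups in step 5. It is therefore an upper bound on the number who met a fixed door and were not debriefed.

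**The case against.** The strongest case on the other side is that the passages are consistent, no number is wrong, the feedback itself is accurate, and what goes undisclosed is mostly how topics in a game were selected. Weighing that is ordinarily a matter for the ethics committee. This stands as an argument about severity. It does not remove the gap, because the protocol itself adopted debriefing as the safeguard.

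A reader might infer four stronger things that the documents do not support:

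- *That every randomised woman is deceived.* Doors appear only when results are sent, which section 3 expects about three weeks into a round, and results may go unopened or be skipped.
- *That the protocol breaks its own written standard.* The sentence in section 13 about telling participants of inaccuracies afterwards is form template wording. The protocol replies that nothing it tells participants is inaccurate, and the template does not clearly reach an undisclosed selection mechanism behind accurate feedback.
- *That the women missed are those who left out of discomfort.* Section 4 names discomfort as a risk, but no reasons for dropout are given, and learning about the doors would not relieve that discomfort.
- *That these women are certainly never told.* Section 6 (Informed Consent) says the consent form and Terms of Service are attached separately. They are not shown and might provide another route.

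It is also fair to say that the destruction rule sets no date and does not prevent a message being sent beforehand. It does not require one either.

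**Conclusion.** The point holds in a limited form. On the text shown, completing the post-Round 8 survey is the only stated trigger for debriefing about the doors, the randomisation and the research questions, and identifiers may be destroyed whether or not it has happened. Randomised non-completers have no stated route.

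The size is unknown: at most 50 to 150 of 500 women under assumed non-completion of 10% to 30%, with fewer having met a fixed door. The conclusion assumes that the separate consent documents contain no other route.

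Severity is minor. A reader might take this as a threat to the trial's results. It is not, because debriefing comes after the outcome questions and the gap does not bias the efficacy analysis.

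**What to change.** - Keep the on-screen debriefing for women who complete the survey.
- In section 3 (both places), section 12 and section 13, add that after the follow-up survey window closes, the Appendix D statement is sent to every randomised participant who has not completed the survey, through the email and text channel already used for round results. The timing must be explicit. Debriefing at enrolment in Round 3 would reveal the fixed doors before they are used and defeat the concealment.
- In section 5, make destruction of identifiers conditional on that message having been sent.
- Check the separate consent form for any existing commitment, so that the documents agree.

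The cost is a short amendment, one automated message and light rewording of the statement's opening, which is written for a survey screen. Contact details are held slightly longer. Concealment during play and the outcome data are unaffected, because the message goes out after follow-up has closed.

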14. QUESTIONNAIRES AND SURVEYS

Include copies of questionnaires or survey instruments with the application (draft form is acceptable).

If not yet developed, please so indicate and provide the Committee with an outline of the general topics that will be covered. Also, when the questionnaire or interview schedule has been compiled, it must be submitted to the Committee for separate review and approval. These instruments must be submitted for approval prior to their use.

Consider your population. If they are foreign speakers, please include copies in the foreign language.

See APPENDIX C for questions to be asked in LezParlay rounds, and APPENDIX D for the post-competition feedback survey to be completed by Evaluation Study participants.

15. PHYSICIAN INTERACTIONS

To ensure that all patients receive coordinated care, the principal investigator is obligated to inform the primary physician (when not the principal investigator) of all studies on his/her patients.

N/A

16. SUBJECT SAFETY

Describe provisions, if appropriate, to monitor the research data collected, to ensure continued safety to subjects.

N/A

17. REDUNDANCY

To minimize risks to subjects, whenever appropriate, use procedures already being performed on the subjects for diagnostic or treatment purposes. Describe provisions.

N/A

18. COUNSELING

In projects dealing with sensitive topics (e.g., depression, abortion, intimate relationships, etc.) appropriate follow-up counseling services must be made available to which subjects might be referred.

The IRB should be notified of these services and how they will be made available to subjects.

N/A

19. SAFEGUARDING IDENTITY

When a research project involves the study of behaviors that are considered criminal or socially deviant (i.e., alcohol or drug use) special care should be taken to protect the identities of participating subjects.

In certain instances, principal investigators may apply for "Confidentiality Certificates" from the Department of Health and Human Services or for "Grants of Confidentiality" from the Department of Justice.

N/A... All participants in this study will be of the legal drinking age.

20. ADVERTISEMENTS

If advertisements for subjects are to be used, attach a copy and identify the medium of display.

See Appendix A for recruitment/promotional ads.

21. FOREIGN RESEARCH

When research takes place in a foreign culture, the investigator must consider the ethical principles of that culture in addition to the principles listed above.

N/A

22. EXEMPTION CATEGORIES (45 CFR 46.101(b) 1-6)

If you believe your study falls into any of the Exemption Categories listed below, please explain which category(ies) you believe it falls into and why.

- 1) Research conducted in established or commonly accepted educational settings, involving normal educational practices, such as (i) research on regular and special instructional strategies, or (ii) research on the effectiveness of or the comparison among instructional techniques, curricula, or classroom management methods.
- 2) Research involving the use of educational tests (cognitive, diagnostic, aptitude, achievement), if information taken from these sources is recorded in such a manner that subjects cannot be identified, directly or through identifiers linked to the subjects.
- 3) Research involving survey or interview procedures, except where all of the following conditions exist: (i) responses are recorded in such a manner that the human subjects can be identified, directly or through identifiers linked to the subjects, (ii) the subject's responses, if they became known outside the research, could reasonably place the subject at risk of criminal or civil liability, or be damaging to the subject's financial standing, employability, or reputation, and (iii) the research deals with sensitive aspects of the subject's own behavior, such as illegal conduct, drug use, sexual behavior, or use of alcohol.

All research involving survey or interview procedures is exempt, without exception, when the respondents are elected or appointed public officials, or candidates for public office.

- 4) Research involving the observation (including observation by participants) of public behavior, except where all of the following conditions exist: (i) observations are recorded in such a manner that the human subjects can be identified, directly or through the identifiers linked to the subjects, (ii) the observations recorded about the individual, if they became known outside the research, could reasonably place the subject at risk of criminal or civil liability, or be damaging to the subject's financial standing, employability, or reputation, and (iii) the research deals with sensitive aspects of the subject's own behavior such as illegal conduct, drug use, sexual behavior, or use of alcohol.
- 5) Research involving the collection or study of existing data, documents, records, pathological specimens, or diagnostic specimens, if these sources are publicly available or if the information is recorded by the investigator in such a manner that subjects cannot be identified, directly or through identifiers linked to the subjects.

6) Unless specifically required by statute (and except to the extent specified in paragraph (1)), research and demonstration projects which are conducted by or subject to the approval of the Department of Health and Human Services, and which are designed to study, evaluate, or otherwise examine: (i) programs under the Social Security Act or other public benefit or service programs, (ii) procedures for obtaining benefits or services under those programs, (iii) possible changes in or alternatives to those programs or procedures, or (iv) possible changes in methods or levels of payment for benefits or services under those programs.

N/A

Please deliver to: [name], IRB Coordinator, [name] or [contact].

